7.2 Study endpoint

Co-primary endpoint and evaluation criteria:

(1) The HI antibody GMTs and SCRs for each of the four strains in QIV groups were inferior to those of control groups at 28 days after vaccination in total populations. The non-inferiority criteria are as follows:

- **GMTs:** Non-inferiority of GMTs was demonstrated if the lower limit of the two-sided 95% confidence interval (CI) for adjusted GMT ratio (test group/control group) $\geq 2/3$ for each of the four strains.
- **SCRs:** The percentages of participants with either a pre-vaccination titer $<1:10$ and a post-vaccination titer $\geq 1:40$, or a pre-vaccination titer ≥ 10 and a ≥ 4 -fold increase in post-vaccination titer at 28 days after vaccination. Non-inferiority for SCR was demonstrated if the lower limit of the two-sided 95% CI for SCR difference (test group-control group) was $\geq -10\%$ for each of the 4 strains.

(2) The SCRs and SPRs should meet the absolute criteria in total populations.

- Absolute criteria of SCR and SPR: the lower limit of the two-sided 95%CI for SCR was $\geq 30\%$; the lower limit of the two-sided 95%CI for SPR was $\geq 60\%$.

Second endpoint and evaluation criteria:

➤ **Immunogenicity endpoint**

(1) The HI antibody GMTs and SCRs for the unique B strain in QIV groups were superior to those of control groups at 28 days after vaccination in total populations. The criteria for superiority were as follows:

- The lower limit of the two-sided 95%CI for adjusted GMT ratio (test group/control group) ≥ 1.5 ;
- The lower limit of the two-side 95% CI for SCR difference (test group-control group) was $\geq 10\%$.

(2) The HI antibody GMTs and SCRs for each of the four strains in 0.5mL-dose QIV group were inferior to those of 0.25-mL-dose QIV at 28 days after vaccination in total populations. The non-inferiority criteria were consistent with the co-primary endpoints.

(3) The HI antibody GMIs of each strain at 28 days after second vaccination in total population;

(4) The HI antibody SCRs, SPRs, GMTs and geometric mean fold increasing (GMFIs) of 0.5mL-dose QIV and 0.25mL-dose QIV in susceptible population (HI antibody titers $<1:10$). The non-inferiority, superiority and absolute criteria refer to the total population.

➤ **Safety endpoint**

- (1) Incidence of adverse reactions in 0-28 days after each dose of QIVs;
- (2) Incidence of adverse reactions in 0-7 days after each dose of QIVs;

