2.3 Changes in the Planned Analysis

There are no changes to the analyses planned in the protocol.

3 Study Objective, Estimand, and Endpoint

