3.1.2 Secondary Objective

- To evaluate the non-inferiority of immunogenicity in participants aged 6-35 months after 2 doses of 0.5mL-dose QIV compared with 0.25mL-dose QIV for each strain, in terms of SCR and GMT of HI antibody;
- To evaluate the superiority of immunogenicity in participants aged 6-35 months after 2 doses of 0.25mL-dose or 0.5mL-dose QIVs compared with two TIVs (including BV or BY) for the unique strain, in terms of SCR and GMT of HI antibody;
- To evaluate the immunogenicity in participants aged 6-35 months after vaccination of 2 doses of 0.25mL-dose or 0.5mL-dose QIVs;

- To evaluate the safety of 0.25mL-dose or 0.5mL-dose QIVs in participants aged 6-35 months.

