Susceptible population: HI antibody titer $<1:10$ before immunization

Non-susceptible population: HI antibody titer $\geq 1:10$ before immunization

Seroconversion: HI antibody titer $<1:10$ before immunization, and the antibody titer $\geq 1:40$ after immunization, or

HI antibody titer $\geq 1:10$ before immunization, and the antibody titer after immunization increased ≥ 4 folds.

Protection: HI antibody titer $\geq 1:40$ as the limit of protective antibody

Table 3.2.1.2 Intercurrent Events and Treatment Strategies of Primary Estimand

3.2.2 Secondary Estimand 1

Table 3.2.2.1 Secondary Estimand 1

Secondary Estimand 1	
Population	The target population involves all participants aged 6 to 35 months who have completed two doses of vaccination.
Variable	(1) Whether the H1N1, H3N2, BV, and BY HI antibodies are seroconverted in both the test group 2 (0.5mL) and the test group 1 (0.25mL) 28 days after the second dose. (2) H1N1, H3N2, BV, and BY serum HI antibody titers of the test group 2 (0.5mL) and the test group 1 (0.25mL) 28 days after the second dose.
Treatments	As the same as the primary estimand
Intercurrent Events and Treatment Strategies	As the same as the primary estimand
Population-level Summary	(1) Difference between the SCRs of H1N1, H3N2, BV, and BY serum HI antibodies of the test group (0.5mL) and the test group (0.25mL) 28 days after the second dose. (2) GMT ratios of H1N1, H3N2, BV, and BY serum HI antibodies between the test group (0.5mL) and the test group (0.25mL) 28 days after the second dose.

3.2.3 Secondary Estimand 2

Table 3.2.3.1 Secondary Estimand 2

Secondary Estimand 2	
Population	The target population involves all participants aged 6 to 35 months who have completed two doses of vaccination.
Variable	
(1) Whether the BV HI antibody is seroconverted in the test group (0.5mL or 0.25mL) and the TIV-BY group 28 days after the second dose.
 
(2) Whether the BY HI antibody is seroconverted in the test group (0.5mL or 0.25mL) and the TIV-BV group 28 days after the second dose.

Secondary Estimand 2	
	(3) BV HI antibody titers of the test group (0.5mL or 0.25mL) and the TIV-BY group 28 days after the second dose. (4) BY HI antibody titers of the test group (0.5mL or 0.25mL) and the TIV-BV group 28 days after the second dose.
Treatments	As the same as the primary estimand
Intercurrent Events and Treatment Strategies	As the same as the primary estimand

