- ✓ If the lower limit of the two-sided 95%CI of SCR difference for 28d post-total vaccination serum HI antibody between the two groups (test group 1-pooled control group) and (test group 2-pooled control group) for this type is $\geq -10\%$, the post-vaccination SCR of the test group for this type can be considered to be non-inferior to that of the pooled control group. Otherwise, the non-inferiority test is considered to have failed.

✧ Analysis of post-vaccination antibody SPR

The post-vaccination antibody SPR in all populations, 28d post-total vaccination serum HI SPR in the susceptible population, and the 28d post-total vaccination serum HI SPR in the non-susceptible population, and the 28d post-total vaccination serum HI SPR in the population of <40 before vaccination, and the 28d post-total vaccination serum HI SPR in the population of ≥ 40 before vaccination under the H1N1 and H3N2 types in test group 1, test group 2, and pooled control group will be analyzed using the same statistical methods as those used for post-vaccination SPR.

If the lower limit of the two-sided 95%CI for the 28d post-total vaccination serum HI SPR of the test group for this type is $\geq 60\%$, this type has reached the absolute standard for SPR.

✧ GMT and GMI analysis

In PPS analysis, the covariance analysis model will be employed to analyze the antibodies under H1N1 and H3N2 types, respectively. After logarithmic transformation, the serum HI GMT 28d post-vaccination will be fitted to the covariance analysis model for analysis, with the serum HI GMT 28d post-vaccination after logarithmic transformation as a dependent variable of the model, the logarithmic transformation value of pre-vaccination serum HI antibody GMT as a covariate of the model, and groups will be the fixed effect in the model. The post-vaccination logarithmic transformation value of each group and the least square mean of the difference between groups will be calculated based on the

model. After inverse logarithmic transformation, the post-vaccination antibody corrected geometric mean based on the least square mean of each group, the corrected ratio between groups (test group 1/pooled control group), (test group 2/pooled control group), (test group 1/test group 2), and their 95%CIs will be calculated.

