In the mFAS and FAS analyses, the missing data in 28d post-total vaccination serum HI antibody will be imputed using the multiple imputation method, and each imputed dataset will be statistically analyzed using the same covariance analysis model as in the PPS analyses. The analytical results of the imputed datasets will be pooled using Rubin's method and inverse-logarithmically transformed to obtain the corrected GMT for each group, corrected GMT ratio between each pair of groups, and corresponding 95%CIs.

If the lower limit of the two-sided 95%CI for (test group 1/pooled control group) and (test group 2/pooled control group) is $\geq 2/3$, the post-vaccination antibody GMT of the test group for this type is considered to be non-inferior to that of the pooled control group. Otherwise, the non-inferiority test is considered to have failed.

The same method as mentioned above will be adopted to perform a logarithmic transformation on the GMT of serum HI antibody in the susceptible population 28d post-total vaccination, and then fit the covariance analysis model for analysis.

Meanwhile, in the PPS analysis, all population, susceptible population, non-susceptible population, population of <40 before vaccination and population of ≥ 40 before vaccination under the H1N1 and H3N2 types in the test group 1, test group 2, and pooled control group will be statistically described in terms of HI antibody GMT and GMI, respectively, and the group differences will be statistically examined by using the ANOVA with logarithmic transformation. Meanwhile, the 28d post-total vaccination antibody's GMT/GMI ratio and corresponding 95%CIs will be calculated for the two groups, and the inter-group difference will be statistically tested by t-test after logarithmic transformation.

In the mFAS and FAS analyses, the missing data in the post-vaccination antibodies will be imputed using the multiple imputation method, and each imputed dataset will be statistically analyzed using the same method as in the PPS analysis. The analytical results of the imputed datasets will be pooled using Rubin's method and inverse-logarithmically transformed to obtain the GMT for each group, the GMI for each group, the GMT ratio between each pair of groups, the GMI ratio between each pair of groups, as well as their corresponding 95%CIs.

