- ✓ If the lower limit of the two-sided 95%CI of SCR difference for 28d post-total vaccination serum HI antibody between the two groups (test group 1-control group 1) and (test group 2-control group 1) for this type is $\geq -10\%$, the post-vaccination SCR of the test group for this type can be considered to be non-inferior to that of the control group 1. Otherwise, the non-inferiority test is considered to have failed.

✧ **Analysis of post-vaccination antibody SPR**

The post-vaccination antibody SPR in all populations, 28d post-total vaccination serum HI SPR in the susceptible population, and the 28d post-total vaccination serum HI SPR in the non-susceptible population, and the 28d post-total vaccination serum HI SPR in the population of <40 before vaccination, and the 28d post-total vaccination serum HI SPR in the population of ≥ 40 before vaccination under the H1N1 and H3N2 types in test group 1, test group 2, control group 1 and control group 2 will be analyzed using the same statistical methods as those used for post-vaccination SPR. If the lower limit of the two-sided 95%CI for the 28d post-total vaccination serum HI SPR of the test group for this type is $\geq 60\%$, this type has reached the absolute standard for SPR.

✧ **GMT and GMI analysis**

In PPS analysis, the covariance analysis model will be employed to analyze the antibodies under the BV type in the test group 1, test group 2, control group 1, and control group 2, respectively. After logarithmic transformation, the serum HI GMT 28d post-vaccination will be fitted to the covariance analysis model for analysis, with the serum HI GMT 28d post-vaccination after logarithmic transformation as a dependent variable of the model, the logarithmic transformation value of pre-vaccination serum HI antibody GMT as a covariate of the model, and groups will be the fixed effect in the model. The post-vaccination logarithmic transformation value of each group and the least square mean of the difference between groups will be calculated based on the model. After inverse logarithmic transformation, the post-vaccination antibody corrected geometric mean based on the least square mean of each group, the corrected ratio between groups (test group 1/control group 1), (test group 2/control group 1), (test group 1/control group 2), (test group 2/control group 2) and (test group 1/test group 2) and their 95%CIs will be calculated.

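### SAP 6.8 prints the adjusted dose GMT ratio as 0.25 mL over 0.5 mL, the reciprocal of the planned 0.5 mL versus 0.25 mL non-inferiority comparison

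*SAP*

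**What the plan says.** SAP 4.3 fixes the labels: test group 1 is the 0.25 mL QIV and test group 2 the 0.5 mL QIV.

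The dose comparison has one direction wherever it is defined:

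- SAP 3.1.2, matching protocol 6.2, sets non-inferiority "after 2 doses of 0.5mL-dose QIV compared with 0.25mL-dose QIV for each strain".
- SAP 3.2.2 (Secondary Estimand 1) summarises it by "GMT ratios of H1N1, H3N2, BV, and BY serum HI antibodies between the test group (0.5mL) and the test group (0.25mL)", with 0.5 mL named first.
- Protocol 7.2, second endpoint (2), has 0.5 mL as subject and 0.25 mL as comparator, and adds: "The non-inferiority criteria were consistent with the co-primary endpoints". The co-primary criteria are a lower 95% limit of at least 2/3 for the adjusted test/control GMT ratio and of at least -10% for the SCR difference.

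SAP 2.3 declares: "There are no changes to the analyses planned in the protocol".

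The ratios actually listed in SAP 6.8 run the other way. For H1N1 and H3N2, "test group 2/pooled control group), (test group 1/test group 2), and their 95%CIs will be calculated". For BV the list ends with "test group 1/test group 2) and their 95%CIs will be calculated". The 2/3 rule written after the first list covers only "the lower limit of the two-sided 95%CI for (test group 1/pooled control group) and (test group 2/pooled control group)", and the BV rule likewise names only test/control ratios.

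**The concern.** The imported criterion needs 0.5 mL in the numerator, and the SAP puts it in the denominator. Every 2/3 decision written out in 6.8 applies the lower limit directly to a ratio as printed. An analyst who does the same with the dose ratio tests whether 0.25 mL is non-inferior to 0.5 mL.

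Nothing else in the visible analysis text corrects this. The eight hypotheses in SAP 6.7 include no dose hypothesis. The mFAS and FAS paragraphs refer to pairs of groups without a direction. The printed ratio is therefore the only explicit numerator and denominator that SAP 6.8 gives for this contrast.

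The misreading matters most where results are most likely to fall. Protocol 2.4 cites studies in which full-dose vaccine improved the immune response in children under 3, so 0.5/0.25 ratios above 1 are the expected side. There the misapplied rule can fail a dose that is doing better than its comparator. On the other side it can pass a dose that should fail.

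**Working it through.** **Inputs.** GMT margin 2/3, or -0.176 on the log10 scale; one-sided alpha 0.025; SD 0.7 for log10 titre; 99% power per serotype; 1,100 per QIV arm; about 17% dropout (all protocol 7.1.2 and SAP 4.3). Evaluable per arm: 1,100 × 0.83 = 913.

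**The plan's own GMT figures.** These confirm the scale and SD.

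- 1:1: n = 2 × 0.7² × (1.960 + 2.326)² / 0.176², which gives 582 per group, as stated.
- 2:1: the same formula with factor 1.5 gives 436 control and 872 test, against the stated 437 and 874. Noncentral-t power at 437/874 is 99.0%.

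The documents give no sample size or power for the dose comparison itself.

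**Relation between the two ratios.** Let R be the observed 0.5/0.25 ratio. The lower limit for R equals 1 divided by the upper limit for 1/R. So a lower limit of at least 2/3 on test group 2/test group 1 is the same as an upper limit of at most 1.5 on test group 1/test group 2.

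**Where the verdicts part.** SE = 0.7 × √(2/913) = 0.03276, and 1.96 × SE = 0.06421.

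- As planned, pass if log10 R - 0.06421 ≥ -0.17609, so R ≥ 10^(-0.11188) = 0.773.
- With the 2/3 lower limit on the printed ratio, pass if -log10 R - 0.06421 ≥ -0.17609, so R ≤ 10^(0.11188) = 1.294.

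Between 0.773 and 1.294 both readings pass. Outside that range they disagree.

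| Setting | SE | Readings agree for R between |
|---|---|---|
| 913 per arm, SD 0.7 | 0.03276 | 0.773 and 1.294 |
| 1,100 per arm, SD 0.7 | 0.02985 | 0.763 and 1.311 |
| 913 per arm, SD 0.5 (assumed, after baseline adjustment) | 0.02340 | 0.741 and 1.350 |

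**Worked cases** (913 per arm, SD 0.7; interval = 10^(log10 R ± 0.06421)).

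| Observed 0.5/0.25 (95% CI) | As planned | Printed 0.25/0.5 (95% CI) | 2/3 lower limit on printed ratio |
|---|---|---|---|
| 1.35 (1.164 to 1.565) | pass | 0.741 (0.639 to 0.859) | fail |
| 0.70 (0.604 to 0.812) | fail | 1.429 (1.232 to 1.656) | pass |

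**Chance of a false failure per strain**, if the rule is misapplied: 1 - Φ((0.17609 - log10 R)/0.03276 - 1.96), with R now the true ratio. The true ratios are assumptions.

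| True 0.5/0.25 ratio | Planned test passes | False failure |
|---|---|---|
| 1.10 | about 100% | 1.6% |
| 1.20 | about 100% | 16% |
| 1.30 | about 100% | 53% |
| 1.40 | about 100% | 85% |

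In the other direction, at a true ratio of 2/3 the planned test passes 2.5% of the time and the misapplied one about 100%.

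**The case against.** The strongest reply is that no visible rule puts 2/3 on the printed dose ratio. SAP 6.8 only lists it for calculation, and each 2/3 rule there names the ratios it governs. The sole rule for this contrast is in protocol 7.2, with 0.5 mL as subject. The listed order may simply follow group number. The interval inverts exactly, so nothing is lost, and a reader who sees 0.741 (0.639 to 0.859) for 0.25/0.5 can tell that 0.5 mL is higher. The documents give no expected 0.5/0.25 ratio, and at a true 1.10 the false-failure risk is only 1.6%.

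All of that is true, and it limits the consequence. It does not remove the mismatch: the one dose ratio that 6.8 specifies runs against the SAP's own objective, and the equivalent upper-limit rule of 1.5 is stated nowhere visible.

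Two further limits apply.

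- Protocol 7.2 literally says GMTs and SCRs "in 0.5mL-dose QIV group were inferior to those of 0.25-mL-dose QIV at 28 days after vaccination in total populations". The co-primary sentence has the same slip, and 0.5 mL is the subject either way, so this does not change the direction.
- The body of SAP 6.11 is not in the text available, the TFL shells are a separate attachment (SAP 2.1), and protocol 9.11 is untranslated. If any of these sets the direction correctly, it conflicts with 6.8, which would still need correcting.

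**Conclusion.** The concern holds. For H1N1, H3N2 and BV the adjusted dose ratio is printed as the reciprocal of the planned comparison, while the SAP declares no change from the protocol.

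The damage is conditional on the 2/3 lower limit being applied to the ratio as printed. In that case, with 913 per arm and SD 0.7, the GMT verdict reverses for observed 0.5/0.25 ratios below 0.773 or above 1.294. The range of agreement is somewhat wider with all 1,100 per arm or a smaller SD.

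This is a secondary endpoint, and the co-primary conclusions are unaffected. No reversed SCR difference is printed, and none is claimed. BY is not explicit: SAP 6.8(3) applies the BV method to test groups against control group 2 and does not mention a dose ratio. The point should be corrected, but it does not threaten the trial.

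**What to change.** In the GMT paragraphs of SAP 6.8(1) and 6.8(2), do one of the following:

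- print the dose ratio as test group 2/test group 1 and state that 0.5 mL is non-inferior if the lower 95% limit is at least 2/3; or
- keep the printed ratio and state that 0.5 mL is non-inferior if its upper 95% limit is at most 1.5.

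In the same edit, state the SCR contrast as test group 2 minus test group 1 with a lower 95% limit of at least -10%, as protocol 7.2 and SAP 3.2.2 imply. Confirm that the same contrasts and direction apply to BY and to the mFAS and FAS analyses.

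The cost is a few words and one reversed contrast in the program. It needs no further data and does not touch the co-primary analyses.

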5.3 Control Vaccines

The control vaccines (Anflu) are trivalent influenza virus split vaccines prepared with the strains recommended by WHO for the 2023-2024 Northern Hemisphere influenza season. Control Vaccine 1 is the marketed Anflu for the 2023-2024 influenza season, containing 7.5 μ g each of H1N1, H3N2, and BV antigens. Control Vaccine 2 contains 7.5 μ g each of H1N1, H3N2, and BY antigens. The sources of antigen strains for each type in the control vaccines are consistent with those corresponding to the quadrivalent influenza vaccine. The control vaccines are prepared by Sinovac Biotech Co., Ltd., packaged in pre-filled syringes, with a dose of 0.25ml per syringe, and have been inspected by the National Institutes for Food and Drug Control, meeting the requirements of the Manufacturing and Inspection Procedures for Influenza Virus Split Vaccine.

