4.3 Sample Size

This trial requires the test group: ① the non-inferiority comparison with the control groups is established and the next statistical test is carried out; ② when the absolute criteria of SCR and SPR are achieved, the trial can be considered as successful and a positive conclusion can be drawn for the test group. In this trial, when evaluating between the test group 1 (0.25-mL QIV) and test group 2 (0.5mL-QIV), the strategy of sequential test is adopted. First, test group 2 is evaluated. If the positive conclusion of test group 2 is established, test group 1 is further evaluated. Therefore, class I error correction is no longer carried out. The sample size of phase III clinical trials is estimated first by non-inferiority design, namely the QIV group is non-inferior to the TIV group. The primary endpoints of this study include two indicators: SCR and GMT. Only when the SCR and GMT of four serotypes in test group are non-inferior to the control vaccine, the investigational vaccine is considered to be non-inferior to the control vaccine. The total power is 80%, the type II error is 0.2. Based on the different sample size requirements of the two indicators, the type II error is allocated, with 0.16 for SCR comparison and 0.04 for GMT comparison.

(1) Calculation of sample size with the SCR as the indicator:

According to the results of the previous Anflu phase IV clinical trial and other literature, the SCR of the types contained in the vaccine 28 days after vaccination is over 65%, which is used as the reference proportion to estimate the sample size. The test level is taken as one-sided $\alpha=0.025$, the power of non-inferiority comparison for the SCR of a serotype is taken as $1-\beta1/4=1-0.16/4=96\%$, and the non-inferiority threshold Δ is taken as -10%. When comparing the non-inferiority of BY or BV strain, NT:NC=2:1, and PASS software is used to calculate the sample size, the test group needs 914 samples and the control group needs 457 samples. When the non-inferiority test of H1N1 or H3N2 strain is carried out, two control groups are pooled. The sample size ratio of the test group and the pooled control group is 1:1, and the test group and the pooled control group need 625 participants.

(2) Calculation of sample size with the GMT as the indicator:

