Using the antibody GMT 28 days after vaccination as the outcome measure, the non-inferiority margin is $\geq 2/3$ of the 95%CI lower limit of GMT ratio between the test group and the control group, and the non-inferiority margin after logarithmic conversion is $\Delta=-0.176$. The test level is taken as one-sided $\alpha=0.025$, and the power of a certain serotype GMT for non-inferiority comparison is taken as $1-\beta2/4=1-0.04/4=99\%$, and the standard deviation after logarithmic transformation is taken as $\sigma = 0.7$ with

reference to the previous research results. When comparing the non-inferiority of BY or BV, NT:NC=2:1, and PASS software is used to calculate the sample size, the test group needs 874 samples and the control group needs 437 samples. When the non-inferiority test of H1N1 or H3N2 type is carried out, two control groups are pooled. The sample size ratio of the test group and the pooled control group is 1:1, and the test group and the pooled control group need 582 participants each.

When the SCR and GMT of the test group reach the hypothesis of non-inferiority, the absolute criteria of the SCR and seroprotection rate (SPR) of the test group are further hypothesized for test. The trial requires that the SCR and SPR of the four strains of immune antibodies reach the absolute criteria, and the total power of the trial is 80%, so the power of each test is $1 - (0.2/8) = 0.975$.

(3) Calculation of sample size with the absolute criteria of SCR:

Assuming that the SCR after vaccination is 65%, the test level is one-sided $\alpha=0.025$, the lower limit of the confidence interval of the SCR should be greater than 30%, and the power of each test is 97.5%. The sample size is calculated by PASS software, and the test group needs 28 samples.

(4) Calculation of sample size with the absolute criteria of SPR:

Assuming that the SCR after vaccination is 75%, the test level is one-sided $\alpha=0.025$, the lower limit of the confidence interval of the SPR should be greater than 60%, and the power of each test is 97.5%. The sample size is calculated by PASS software, and the test group needs 146 samples.

In consideration of the above the maximum sample size and the dropout rate of about 17%, the sample size of each test group is 1,100, and the sample size of each control group is 550, with a total sample size of 3,300.

5 Analysis Sets

(1) Immunogenicity Analysis Set

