6.8 Immunogenicity Evaluation

Immunogenicity analysis will be based on mFAS, PPS, and FAS. The analysis based on the FAS will not take into account the intercurrent events "early discontinuation of treatment due to loss of visits, withdrawal of informed consent, etc., and failure to complete the full-course vaccination". In addition, if the antibody test result is " $<1:10$ ", it is counted as "5". If the antibody test result is " $>1:10240$ ", it is counted as "10241".

(1) Immunogenicity will be compared between the test group and a pooled trivalent control group of two different sizes for H1N1 and H3N2 types, respectively.

✧Analysis of post-vaccination SCR

In the PPS analysis, the 28d post-total vaccination serum HI SCR in all populations, the 28d post-total vaccination serum HI SCR in the susceptible population, and the 28d post-total vaccination serum HI SCR in the non-susceptible population will be calculated in the test group 1, test group 2, and pooled control group under the H1N1 and H3N2 types, respectively, and the two-sided 95%CIs will be calculated using the Clopper-Pearson method. Meanwhile, the Miettinen & Nurminen method will be used to calculate the two-sided 95%CI of the inter-group rate difference, and the Chi-square test/Fisher's exact test will be used for the statistical test of inter-group difference.

In the mFAS and FAS analyses, multiple imputation methods will be used to impute in the missing data in the post-vaccination antibodies, and the 28d post-total vaccination serum HI SCR in all populations, the 28d post-total vaccination serum HI SCR in the susceptible population, and the 28d post-total vaccination serum HI SCR in the non-susceptible population will be calculated for all populations in the test group 1, test group 2, and combined control group under the H1N1 and H3N2 types, respectively based on the imputed datasets. The analysis results of pooled post-imputed datasets will be pooled using Rubin's method to obtain the pooled SCR, the difference in rates between the two groups, and their 95%CIs for each group. If the CI for pooled rate or rate difference is not estimable, the rate or rate difference and its 95%CI will be estimated using the Bootstrap method, which will be sampled 1,000 times with putbacks and seeded = 111.

- ✓ If the lower limit of the two-sided 95%CI for the 28d post-total vaccination serum HI SCR of the test group for this type is $\geq 30\%$, this type has reached the absolute standard for SCR.

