Immunogenicity will be compared between the test group (test group 1 or test group 2) and control group 2 for BY types, respectively, using the same method as for BV types.

Forest plots of the SCR, SPR, and GMT of HI antibody of each serotype in all populations 28d post-total vaccination will be plotted.

Sensitivity Analysis: In mFAS analysis, the missing data in the serum HI antibody and SCR of HI antibody 28d post-total vaccination will be analyzed for sensitivity analysis by using the Tipping Point Analysis (TPA) and the Jump to Reference (J2R) method based on δ adjustment. Evaluate the robustness impact of missing data on the test results. For details, please refer to Section 6.10 on the handling of Missing Data.

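### The B-strain GMT covariance model, as written, includes an arm that received no antigen of that lineage and gives it about one sixth of the residual variance behind a co-primary non-inferiority interval

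*SAP*

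**What the plan says.** - **Model for BV.** SAP 6.8(2), under GMT and GMI analysis, applies a covariance model to "antibodies under the BV type in the test group 1, test group 2, control group 1, and control group 2, respectively". Log post-vaccination titre is the response, log baseline titre is the covariate, and "groups will be the fixed effect in the model". Neither a group-by-baseline term nor unequal variances are mentioned.
- **Contrasts.** Adjusted ratios to control group 1 come from the model, and so do ("test group 1/control group 2), (test group 2/control group 2) and (test group 1/test group 2").
- **BY.** SAP 6.8(3) compares each test group with control group 2, "using the same method as for BV types".
- **Decision.** Protocol 7.2 makes the adjusted GMT ratio a co-primary criterion: the lower 95% limit must reach 2/3. SAP 6.8(2) applies this to test group over control group 1, and uses the same model after imputation in the mFAS and FAS.
- **Antigen content.** Protocol 5.3 gives the second control vaccine 7.5 μg "each of H1N1, H3N2, and BY antigens", so it contains no BV. The first control vaccine contains no BY.
- **Planning SD.** In SAP 4.3, "the standard deviation after logarithmic transformation is taken as" 0.7. No separate value is given for an arm without the lineage.

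**The concern.** A covariance model with one residual variance estimates that variance from every arm in the fit. The BV comparison of QIV with TIV-BV would therefore borrow scatter from children who received no BV antigen. Their BV titres are not responses to a BV-containing vaccine. SAP 6.8 also sets every result below 1:10 to 5, which can compress their spread. A smaller SD in that arm is therefore plausible, though the documents do not show it.

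If that arm is less variable and the other three share one SD, the lower limit of the non-inferiority ratio is slightly too high and the component test exceeds 2.5%. The superiority interval against the same arm is then too wide. H1N1 and H3N2 are unaffected, because every arm received those antigens.

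**Working it through.** **Inputs.** From SAP 4.3: arms of 1100/1100/550/550, about 17% dropout, SD 0.7 (log10), margin −0.176, one-sided α 0.025, GMT power 99% per serotype. Analysed numbers: 1100 × 0.83 = 913 and 550 × 0.83 ≈ 457, total 2740. Assumed: *s*, the residual SD in the arm without the lineage, from 0.2 to 0.6, with 0 and 0.8 as further cases.

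**Plan's own figure.** Control n at 2:1 = 1.5 × 0.7² × (1.960 + 2.326)² / 0.176² ≈ 436, so 872 in the test group. The plan states 437 and 874, so its GMT inputs reproduce to within 2.

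**Variance share.** 457/2740 = 16.7%.

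**Non-inferiority interval, other three arms at SD 0.7.**

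- Pooled variance = [(913 + 913 + 457) × 0.49 + 457 × s²] / 2740
- Width factor k = √(pooled variance / 0.49)
- One-sided error at the margin = Φ(−1.96k)

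| s | k | Error |
|---|---|---|
| 0 | 0.913 | 3.68% |
| 0.2 | 0.920 | 3.56% |
| 0.35 | 0.935 | 3.34% |
| 0.5 | 0.958 | 3.02% |
| 0.6 | 0.978 | 2.77% |
| 0.8 | 1.025 | 2.22% |

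**Shift in the lower limit.** The correct half-width is 1.96 × 0.7 × √(1/913 + 1/457) = 0.0786 log10.

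- s = 0.2: the limit rises by (1 − 0.920) × 0.0786 = 0.0063 log10, or 1.5%. The decision changes only if the correct limit lies between 0.657 and 0.667.
- s = 0.6: the rise is 0.4%, and the range is 0.664 to 0.667.

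**Superiority interval against the arm without the lineage.** The correct variance is 0.49/913 + s²/457; the model uses pooled variance × (1/913 + 1/457). At s = 0.2, √(0.001362/0.000624) = 1.48, so 48% too wide. At s = 0.5 it is 17% and at s = 0.6 it is 8%.

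**When the matched TIV arm also differs from 0.7.** Matched TIV SD 0.6 with s = 0.4 gives 2.4%; 0.8 with s = 0.4 gives 4.2%. Dropping the extra arm but keeping one shared variance is not enough: for matched TIV SD 0.6 / 0.8, a three-arm fit gives 1.8% / 3.3% and a two-arm fit 2.0% / 3.0%.

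**Simulation.** 20,000 runs per case at a true ratio of 2/3, Monte Carlo SE about 0.12 points. Residual SD was 0.7 and baseline slope 0.5 in arms given the lineage; slope was 1.0 in the other.

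- Four-arm model, s = 0.2, 0.35, 0.5, 0.6: 3.6, 3.4, 2.9, 2.7% with baseline SD 0.3, and 3.3, 3.3, 2.8, 2.6% with baseline SD 0.6. The slope mismatch partly offsets the smaller scatter.
- Three-arm model with arm-specific variances: 2.4% to 2.6% in the same cases, and 2.5% / 2.4% when the matched TIV SD is 0.6 / 0.8.

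**SCR and GMT together, one B strain.** 60,000 runs at a true ratio of 2/3, comparing the correct interval with the one at s = 0.2. The false-pass rate is 1.3% versus 1.6% if control SCR is 65%, and 2.4% versus 3.4% if it is 85%.

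**The case against.** - **The four-arm fit is an inference.** The same list of arms opens the BV seroconversion paragraph, where inference is pairwise. Section 6.8(2) also carries leftover wording from the H1N1/H3N2 section, and the hypotheses in SAP 6.7 set the test group mainly against the matched control. BY is weaker still, because 6.8(3) names only control group 2. Pairwise fits are therefore possible. However, one model yielding ratios to both controls and between the two test groups reads more naturally as a four-arm fit. If pairwise fits were meant, the SAP still needs to say so.
- **The direction is unknown.** This stands. The documents give no SD for the arm without the lineage, and some plausible patterns leave the error at or below 2.5%.
- **The 4.2% case mixes two problems.** This also stands: 0.8 of its 1.7 excess points remain in a three-arm fit with shared variance, so they come from the difference between the QIV and matched TIV arms.
- **The effect is small.** At a true ratio of 1, the chance that the decision changes is 0.27% (s = 0.2) to 0.09% (s = 0.6). At a ratio of 0.9 it is 2.5% to 0.7%. The overall requirement dilutes it further: "Only when the SCR and GMT of four serotypes in test group are non-inferior to the control vaccine" does the plan accept non-inferiority.
- **The SAP already reports a two-group GMT ratio with a t-test.** That ratio does not borrow variance from the extra arm, but it is unadjusted and is not the decision interval.

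**Conclusion.** The concern holds as a conditional, minor point. On the natural reading of SAP 6.8(2), the non-inferiority interval for a B strain takes one sixth of its residual variance from an arm that did not receive that lineage, and nothing in the plan supports equal variance there. With 913/913/457/457 analysed and SD 0.7 in the other three arms, an SD of 0.2 to 0.6 in that arm gives component error of 3.6% to 2.8%, with a ceiling of 3.7%. The opposite pattern makes the test conservative. The effect on the overall claim is smaller than on this component. Confidence is medium, because the four-arm reading and the smaller SD are both likely but not stated.

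**What to change.** Before database lock, state in SAP 6.8:

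1. Each B-strain non-inferiority model is fitted only on arms that received the lineage: test groups 1 and 2 with control group 1 for BV, and with control group 2 for BY. Residual variances are arm-specific, for example PROC MIXED with REPEATED / GROUP= and Satterthwaite degrees of freedom. A two-arm model of test group and matched control, also with arm-specific variances, is an acceptable alternative.
2. The superiority ratio against the arm without the lineage comes from a separate model with group-specific variance and baseline slope, compared at the overall mean log baseline titre.

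The cost is SAP wording and a few lines of SAS. The non-inferiority intervals may widen slightly. If the arm without the lineage is the less variable one, the superiority intervals become narrower.
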